- 2) Overdose Risk Assessment: This assessment is used to determine the potential for future overdose based on prior overdose history, current drug use practices and social context for current drug use. This assessment is not standardized but is compiled from individual items of known risk factors for overdose.
- 3) World Health Organization Quality of Life (WHOQOL-BREF). This is a short assessment to measure general health and physical, social and emotional functioning.
- 4) World Health Organization Alcohol, Smoking and Substance Involvement Screening Test (WHO-ASSIST v.3). This is a multi-item tool to determine areas of substance use and misuse. This assessment battery screens for recent and lifetime use of a variety of substances, including illicit drugs, alcohol, pharmaceuticals and tobacco products.
- 5) Age of First Use: Subjects are asked to provide the ages they first used a variety of substances.
- 6) HIV Risk Assessment Battery: This assessment is used to determine the potential for contracting HIV, hepatitis and other blood-borne illnesses based on drug use and sexual use behaviors.
- 7) Overdose History: This assessment will collect information related to any prior overdose that the subject has experienced or witnessed.
- 8) EQ-5D-3L: This validated quality of life measure asks about problems in mobility, self-care, usual activities, pain and discomfort, anxiety and depression and overall health.

Locator information:

Subjects will be asked to provide a number of sources to ensure they can be contacted for 3, 6 and 12 month follow-up visits. However, because we anticipate a number of high risk subjects to be indigent, subjects may be enrolled if they provide at least one primary source of locator information.

Randomization

Subjects will be randomized to receive either standard of care or the study intervention. We will recruit equal numbers of subjects in the intervention and control arms of the study, meeting eligibility criteria as heroin user or primarily pharmaceutical opioid users.

Follow-up Visits

Follow-up visits will occur at 3, 6 and 12-month after enrollment. All interviews will be by phone. Most assessments given at the baseline interview will be repeated at each follow-up

point. In addition to the assessments subjects will be asked questions about whether they have naloxone and, if not, what happened to any naloxone that was given to them.

Secondary Data Sources

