Secondary data on health care and drug treatment utilization will be obtained from Washington State (separate IRB action pending) using the following sources:

- Treatment and Assessment Report Generation Tool (*TARGET*) for drug treatment admissions data
- The Comprehensive Hospital Abstract Reporting System (CHARS) for hospital admissions

Information on any ambulance transports will be obtained from the Seattle Fire Department's Medic 1 unit.

In the event of a subject death during the study we will request information on cause of death from the King County Medical Examiner's Office. If a subject cannot be located we will also check this source to see if they have died and if so to obtain data on the cause of death. If we are unable to locate a subject during the course of the study or at final follow-up we will utilize the King County Jail Inmate Look-up Service. At no time will subjects be contacted or study procedures attempted while the subject is incarcerated.

Intervention Description

Standard care for patients who have used opioids would vary according to individual clinical need and might include referral to drug treatment or detoxification services. Standard care would not include OOPEN and BBCC interventions as specified in this grant. After baseline data are obtained subjects assigned to the intervention undergo the following procedures:

A brief behavior change counseling (BBCC) session

- Conveys subjects' risk for overdose, based on the baseline measures
- Engages them in a reflective discussion of the pros and cons of their current patterns of use
- Has the patients identify behavior change(s) they are interested in making to improve their health
- Encourages them to share opioid overdose prevention and intervention information and materials with their family, friends, housemates, and/or drug using partners.

Education and training on opioid overdose prevention and intervention with naloxone (OOPEN)

- Subjects will view a training video on study laptops that reviews:
 - Information on risk factors for overdose and how to prevent and reduce the risk of overdose

- How to recognize an opioid overdose
- The importance of calling 911
- How to intervene in an overdose
 - Positioning a victim in rescue position
 - Brief overview of rescue breathing
 - Training on how and when to administer naloxone

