- Subjects will be given a study brochure that covers the information in the video and reviews the Washington State 911 Good Samaritan overdose law which provides immunity from prosecution for drug possession charges to overdose victims and bystanders who seek aid in an overdose event.
- Prescribing and dispensing overdose rescue kits including 2 doses of intra-nasal naloxone, a disposable rescue breathing mask, and disposable gloves.
- Subjects in the intervention group will be informed that they may have one replacement of the naloxone kit (2 doses) during the 12 month study period.

We expect the intervention to take 30-45 minutes on average based on our experience and that this is feasible and reasonable for subjects and interventionists.

Fidelity assessment for the BBCC will be done with the shortened Motivational Interviewing Treatment Integrity (MITI) instrument.

Schedule of and Sources Data Obtainment

MEASURES	DATA SOURCES AND TIMING					
	Interview			Administrative		
	Case Report Form	Base-line	3 & 6 mos.	12 mo.	Up to 10 yrs.	Up to 10 yrs.
PRIMARY AIMS						
Aim 1: Overdose						
Subject overdosed prior 3/6* months	X		X			
Subject overdosed Y/N & Date						X
Aim 2: Drug use and other overdose risk behaviors						
Alcohol/Drugs 3/6 month use frequency	X		X		X	
Opioid use following interruption past 3/6 months	X		X		X	
Using opioids without others present	X		X		X	
Avg. daily opioid dose- Prescribed Opioid Users	X		X		X	
Opioid substitution drug treatment prior 3/6	X		X		X	
Other drug treatment sought or used prior 3/6	X		X		X	
SECONDARY AIMS						
Aim 3: Health care utilization						

ED, Outpatient, Inpatient and Ambulance- # & Aim 4: Health care costs Hospital-based total direct health care costs			x	x
Aim 5: HIV Risk Behaviors	x	x	x	x
CO-VARIATES & POTENTIAL EFFECT MODIFIERS				
Demographics	x			
Employment, health insurance, income, housing	x	x	x	
Alcohol/Drugs ages of first use	x			
Medical status and satisfaction (WHO QOL BREF, EQ-5D- 3L)	x	x	x	
Behavior change plans and readiness	x			
Overdose lifetime history	x			
Possessed, "carried" naloxone, # of days past 3/6	x	x	x	
Overdose # witnessed events past 3/6 months	x	x	x	
Source of naloxone- Study, other	x	x	x	
Subject had naloxone administered to them, #, by Disposition of naloxone	x	x	x	x
Subject had negative/allergic reaction to naloxone	x	x	x	
FIDELITY ASSESSMENT OF BASELINE				
Overdose prevention & intervention training. Item Motivational Interviewing Treatment Integrity 3.1.1	x			

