Study medication will be ordered, stored, maintained and dispensed by the Investigational Drug Service Pharmacies at Harborview Medical Center and UW Medical Center and the clinical dispensary at Evergreen Treatment Services. Upon receipt, the investigator, pharmacist, or authorized designee is responsible for taking inventory of the investigational agent. A record of this inventory will be kept and usage will be documented. Any unused or expired investigational agent shall be accounted for.

Adverse event reporting

The risks expected from trials employing behavioral interventions are presumed minimal and the medication being prescribed for possible future use is designed to be used to prevent a fatal overdose with side effects being rare. However, given the nature of ongoing drug and/or medication use the population studied in this trial is possibly at risk for an overdose. Adverse events (AEs) will be categorized as serious or non-serious, as related or not related to the study, and as expected or unexpected. An AE is defined as any reaction, side effect, or untoward event that occurs during the course of the clinical trial. Stable chronic conditions, such as substance abuse, which are present prior to clinical trial entry and do not worsen, are not considered AEs. Common, minor ailments and complaints will be excluded from any type of documentation. These may include: colds, flu's, cuts, scrapes, coughs, headaches, stomach complaints, and general fatigue.

Serious adverse events (SAEs) are defined as any fatal event, any immediately life threatening event, any permanent or substantially disabling event, any event that requires or prolongs inpatient hospitalization, congenital anomaly or birth defect, or any event requiring intervention to prevent any of the previously listed serious events. Hospital visits that do not result in admittance are not considered SAE's (e.g. emergency room visit for a non-study-related injury that does not result in admittance). Normal childbirth and pre-planned elective procedures are not considered SAEs. AE/SAE's will be elicited by interventionists/research interviewers at each assessment visit by asking the participants if they have noticed any new problems or existing problems that have gotten worse (using the Adverse Events Worksheet).

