Disclosure of an AE/SAE may also occur in an unsolicited manner to a research or clinical staff member. The interviewers should be focused on gathering data to aid in determining study relatedness. Study-relatedness will be determined by the interviewers in consultation with one of the investigators. All AEs and SAEs will be recorded in the AE/SAE log and entered into the secured project database. AEs that are not study related do not require any further paperwork documentation besides the AE Log. In this study, potential AEs that may be related to the study would be an increase in emotional distress in relation to discussion of past or current drug use behaviors *or side effects of naloxone*.

University of Washington Adverse Events reporting requirements

The term adverse event is generally used to refer to any untoward or unfavorable medical occurrence in a human subject, including any abnormal sign (for example, abnormal physical exam or laboratory finding), symptom, or disease, temporally associated with the subject's participation in the research, whether or not considered related to the subject's participation in the research. Adverse events encompass both physical and psychological harms. They occur

most commonly in the context of biomedical research although, on occasion, they can occur in the context of social and behavioral research.

Unanticipated problems, in general, include any incident, experience, or outcome that meets all of the following criteria:

1. unexpected (in terms of nature, severity, or frequency) given (a) the research procedures that are described in the protocol-related documents, such as the IRB-approved research protocol and informed consent document; and (b) the characteristics of the subject population being studied;
2. related or there is a reasonable possibility that the incident, experience, or outcome may have been caused by the procedures involved in the research; and
3. suggests that the research places subjects or others at a greater risk of harm (including physical, psychological, economic, or social harm) than was previously known or recognized.

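### SAEs are actively sought only by interview, and nothing feeds the planned hospital, ambulance and death records into the SAE log, so events in unreached subjects will be under-counted

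*Combined protocol and SAP*

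**What the plan says.** Adverse event reporting sets the definition: "Serious adverse events (SAEs) are defined as any fatal event, any immediately life threatening event", and also "any event that requires or prolongs inpatient hospitalization". The same section gives the active method of detection: AEs and SAEs "will be elicited by interventionists/research interviewers at each assessment visit by asking the participants if they have noticed any new problems" or existing ones that have become worse. It adds a passive route: "Disclosure of an AE/SAE may also occur in an unsolicited manner to a research or clinical staff member". All AEs and SAEs then go into a log.

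Follow-up Visits places the interviews at 3, 6 and 12 months and states "All interviews will be by phone". Secondary Data Sources says "At no time will subjects be contacted or study procedures attempted while the subject is incarcerated". It also says that cause of death will be requested from the King County Medical Examiner when a subject dies, and that this office will be checked for subjects who cannot be found.

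The trial plans to obtain other records. Secondary Data Sources lists "The Comprehensive Hospital Abstract Reporting System (CHARS) for hospital admissions", among state data described as serving health care and drug treatment utilization and still awaiting a separate IRB action. It also lists ambulance transports. The opening summary adds medical records and death certificates. Refusing access to medical or drug treatment records is an exclusion criterion.

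The oversight committee meets quarterly after the first month and discusses any SAE, to judge whether a change in procedures could modify the risk. The research coordinator prepares its reports.

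**The concern.** Two of the main SAE categories, death and admission, leave a record whether or not the subject can be interviewed. The plan nevertheless looks for them mainly by asking the subject. In a population that the protocol itself expects to be partly indigent and hard to follow, subjects with serious events may well be among those hardest to reach by phone. The records that would show these events are intended for the overdose, utilization and cost aims, and the text gives them no role in safety surveillance.

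At stake is the completeness of the list that the committee uses to decide whether procedures should change. An admission that is never logged cannot be discussed.

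**Working it through.** **1. Events set against the stated routes to the log.**

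| Event | Stated route | What remains uncovered |
|---|---|---|
| Admission, subject interviewed afterwards | Interview question | Recall error; delay until the next call |
| Admission, subject missed at one call but reached later | Later interview | Longer delay; the plan does not say that the later call covers the missed interval |
| Admission, subject jailed at the time of a call | Interview after release | Not captured by interview if never reached after release |
| Admission, subject lost | Unsolicited disclosure only | No record check is stated |
| Death in King County | Medical Examiner check, then the rule that all SAEs are logged | Link to the log is implied, not written |
| Death elsewhere in Washington | Unsolicited disclosure | Death certificates are planned but not tied to the log |

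The last row matters because eligibility extends to residents of the whole state, while the named Medical Examiner's office serves one county.

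**2. Timing.** The committee meets every quarter, but no interview is scheduled between months 6 and 12. An admission just after the month 6 call may wait up to 6 months to be asked about, which spans about two committee meetings.

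**3. Use of records.** Adverse event reporting, Data Safety Monitoring Oversight Committee, Study monitoring and Data monitoring contain no step that compares hospital, CHARS, ambulance or death records with the SAE log.

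**4. Deaths.** Sample Size Calculation puts fatal overdose in heroin users at about 1% a year. With 500 heroin users, 500 × 0.01 = 5 overdose deaths a year. None can be self-reported, so their capture depends on the Medical Examiner check or on someone telling the study. The documents do not say what share would occur outside King County.

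**5. Admissions: an illustration on assumed inputs.** The plan gives no figure for SAE capture, loss to follow-up or admission rate, so there is nothing of its own to reproduce. Let L be the proportion of subjects never reached and k their admission rate relative to reached subjects. The share of admissions missed by interview alone is S = Lk / [(1 − L) + Lk].

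- L = 12.4%: k = 1 gives 12.4%; k = 2 gives 0.248/1.124 = 22.1%.
- L = 20%: k = 1 gives 20.0%; k = 2 gives 0.40/1.20 = 33.3%.
- L = 30%: k = 1 gives 30.0%; k = 2 gives 0.60/1.30 = 46.2%.

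The 12.4% is 1 − 219/250, the margin between the number needed and the number enrolled per arm. It is only a reference point. The plan says the margin serves both power and loss, so it is not a loss rate. Unsolicited disclosure would lower S; recall error among interviewed subjects would raise it.

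**6. Arms: also assumed.** With equal true SAE rates and unequal loss, the apparent ratio (intervention to control) is (1 − L_I)/(1 − L_C). Loss of 10% against 20% gives 0.90/0.80 = 1.13; 15% against 30% gives 0.85/0.70 = 1.21. Nothing in the documents says that loss will differ by arm.

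**The case against.** The strongest case on the other side is that this is a narrow gap in documentation. Interview is not the only route. Deaths are looked for through the Medical Examiner, and a death found there is an SAE that must be logged. The bar on contacting jailed subjects ends at release. The study-related harms that the protocol anticipates, emotional distress and naloxone side effects, are better found by interview than in admission records. No comparison of SAEs by arm is planned, while inpatient admissions (Aim 3) and fatal and non-fatal overdoses (Aim 1) are compared by arm. The committee may also request other reports.

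All of this stands as fact, and it limits the point to admissions of unreached subjects and deaths outside King County. It does not close the gap. The Aim 1 and Aim 3 analyses are not described as feeding the committee's quarterly reports, and the possibility of requesting a report is not a procedure for finding events.

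Three stronger readings are tempting, and the documents do not support them:

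- A reader might infer that the trial already holds admission records for everyone. The state data are planned, with IRB action pending, and the section on other analyses treats the completeness of HMC/UWMC and King County ambulance data as something still to be assessed.
- A reader might infer that dead or jailed subjects contribute almost nothing. The Medical Examiner check and contact after release contradict this.
- A reader might infer that SAE counts cannot be compared by arm because intervention subjects are told "they may have one replacement of the naloxone kit (2 doses) during the 12 month study period" and so have an extra reporting channel. The plan does not say that adverse events are asked about when a kit is replaced, and clinical staff, to whom events may be disclosed, are not confined to one arm.

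**Conclusion.** The concern holds in limited form. Apart from unsolicited disclosure and the King County Medical Examiner check, SAEs are sought only at interview, and no written step reconciles the log with the records the trial plans to obtain. Followed as written, the plan under-counts admissions of subjects who are lost or not reached, and deaths outside King County, in what the committee sees.

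The documents do not allow the size to be determined. The 12% to 46% range for admissions rests on assumed non-contact and relative admission rates and applies to interview alone. An absolute number of missed admissions would need an admission rate that the documents do not give, so none is offered. Imbalance between arms is possible if contact rates differ, but it is not shown. The weakness concerns safety surveillance; the planned efficacy comparisons are not affected by it.

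**What to change.** Add the following to Adverse event reporting, applied identically in both arms:

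- Before each committee report, the research coordinator checks HMC/UWMC admission records, at least for subjects who missed their most recent interview. Qualifying admissions are logged with dates, leaving out childbirth without complications and elective procedures planned in advance, as the SAE definition already does.
- Any death found through the existing Medical Examiner check is entered in the SAE log with its date.
- When CHARS and death-certificate data become available, the log is reconciled against them for all randomized subjects.
- Record-found and interview-reported SAEs are tabulated separately by arm, so that differences in ascertainment can be seen.

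The cost is modest coordinator time and more unrelated admissions in the log. Coverage of admissions outside HMC/UWMC stays incomplete until CHARS data arrive, which depends on the pending IRB action. Subjects must already allow access to their records to enroll and are asked for HIPAA authorization at consent; the team should confirm that this authorization covers safety surveillance.

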The study was powered to address aim 1, the impact of the intervention on non-fatal overdose. For the study of each opioid user type (heroin and pharmaceutical opioids) the number of subjects needed in each arm of the study (intervention and comparison) to achieve power of 0.80 to detect a decline in the overdose rate from 20% to 10% at a confidence level of 0.05, is 219 subjects. To increase power somewhat and account for potential loss to follow up, we plan to enroll more subjects, 250 in each arm of each study, for a total of 500 heroin using subjects and 500 pharmaceutical opioid, non-heroin using subjects. Other outcomes to be analyzed include drug use and services utilization. Data on brief interventions in ED's shows declines in drug use and ED utilization of at least 40%. Specifically in Washington State, the Screening and Brief Intervention Referral and Treatment (SBIRT) found a 45% reduction in average days of drug use among high risk heroin users who received a brief intervention in an ED (from 15.8 days to 8.7 days in the prior month) and 41% reduction among high risk pharmaceutical opioid users (12.8 to 7.5 days).

Assumptions behind the power estimate are based upon an annual rate of non-fatal heroin overdose estimated to be a median of 25% across studies and for fatal overdoses approximately 1%. For the purposes of this sample size estimate we are conservatively assuming a total annual overdose rate for heroin users of 20%. We believe that a reduction of the OD rate by 50% may be possible based on the potential for additive effects of the OOPEN and the BBCC interventions. Preliminary data on overdose rates for pharmaceutical opioid

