abusers (no regular heroin use) indicates a rate approximately half that of heroin users based upon analyses conducted by [name] of interviews from 1,661 clients entering methadone maintenance treatment which indicate a *lifetime* overdose rate for pharmaceutical opioid abusers (25%) that is half the rate of heroin abusers (49%). These findings were extrapolated to a 50% lower rate of *annual* overdose, the validity of which cannot currently be determined, but will be ascertained at the conclusion of this proposed study. We are assuming an annual overdose rate of 10% for pharmaceutical opioid users, or 20% over two years which is the amount of time over which follow up via administrative data will be collected. The power estimates above therefore address one year overdose rates for heroin and 2 years for pharmaceutical opioid users.

Planned methodology

Intent to treat analyses will be the primary analytic approach used to analyze the data resulting from this randomized controlled study. Intent to treat analyses compare those assigned to the intervention group to those in the standard care group, regardless of whether those in the standard care group receive some amount of the intervention.

Planned analyses

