Aim 1 Test whether the intervention group has lower rates of opioid overdose and longer time to occurrence of overdose. Overdose will be ascertained at 12 months via self-report and across at least 24 months via administrative data. Because randomized controlled studies are designed to account for potential confounding factors by distributing confounders, measured and unmeasured, equally across comparison and intervention groups, the initial unadjusted analysis will be a logistic regression analysis comparing the probability of opioid overdose in the two study arms. To examine differences in the time to overdose and to account for time varying covariates, such as overdose risk factors, survival analyses will be conducted with the outcome time to overdose(s). A Cox proportional hazards model will be used to investigate the possible association between these factors and event time. We will use sandwich standard error estimates in all statistical tests. Multivariable logistic regression analyses will be conducted to examine the association between predictors and moderators and of the odds of overdose occurrence. Predictors will include treatment assignment and overdose risk factors such as concomitant drug use, interruption in tolerance and homelessness. Potential effect modification will be assessed by including interaction terms for the treatment assignment by severity of opioid and other substance use as measured by the ASSIST. For the pharmaceutical opioid only group, effect modification by opioid user type will be assessed; opioid user typologies will be based upon which inclusion criteria subjects met.

Aim 2 Test whether the intervention group has fewer overdose risk behaviors. These are measured as both binary and continuous data. Binary data will be examined with logistic

regression and continuous data analyzed with ordinary least-squares regression. Analyses will adjust for the overdose risk behavior level or frequency reported at baseline as a concomitant variable, the outcome is the overdose risk behavior at 12 months, and the primary predictor is the treatment group assignment. We will compute robust standard error estimates for each model and use them in all hypothesis tests and confidence intervals.

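### For pharmaceutical opioid users, doubling a 10% annual overdose rate understates the sample size for 0.80 power: 246 per arm by the plan's own method, not 219; the planned 250 still covers it, with little room for loss

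*Combined protocol and SAP*

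**What the plan says.** The Sample Size Calculation applies one target to both user types: "power of 0.80 to detect a decline in the overdose rate from 20% to 10" per cent, requiring 219 per arm. It then says "we plan to enroll more subjects, 250 in each arm of each study", the surplus being meant both to raise power and to cover loss to follow-up. No loss rate is given.

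For heroin users, the 20% is a one-year rate, called conservative against "an annual rate of non-fatal heroin overdose estimated to be a median of 25% across studies". For pharmaceutical opioid users, the text says "We are assuming an annual overdose rate of 10% for pharmaceutical opioid users, or 20% over two years", and concludes: "The power estimates above therefore address one year overdose rates for heroin and 2 years for pharmaceutical opioid users".

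Under Planned analyses, Aim 1, "the initial unadjusted analysis will be a logistic regression analysis comparing the probability of opioid overdose in the two study arms". The same paragraph says: "Overdose will be ascertained at 12 months via self-report and across at least 24 months via administrative data". The Follow-up Visits section says: "Follow-up visits will occur at 3, 6 and 12-month after enrollment".

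**The concern.** Doubling an annual rate gives the expected number of overdoses per person over two years. It gives the probability of at least one overdose only if nobody overdoses in both years. The first Aim 1 analysis is of that probability, so 20% is the most that a 10% annual risk can produce over two years, and the real figure is lower. A lower control rate and a smaller absolute difference need more people for the same power.

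Pharmaceutical opioid users are half the trial, and the Introduction says that no research on preventing overdose in them has been published. A null result in this stratum would be judged against the stated 0.80. The heroin stratum is not affected, because its 20% is already a one-year figure.

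**Working it through.** **Inputs.** Control rate 10% a year, 50% reduction, power 0.80, significance level 0.05, 219 needed and 250 planned per arm: all from the Sample Size Calculation. Equal allocation: from Randomization. Two-sided testing is inferred, because that is the setting that returns 219.

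**Formulas.** With d = p1 − p2, m = (p1 + p2)/2, zα = 1.960 and zβ = 0.842:

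- Uncorrected: n = [zα√(2m(1−m)) + zβ√(p1(1−p1) + p2(1−p2))]² / d²
- Continuity-corrected: n′ = (n/4)[1 + √(1 + 4/(nd))]²

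**1. The plan's figure, 20% vs 10%.** n = (1.960 × 0.5050 + 0.842 × 0.5000)² / 0.01 = 199.0. Corrected: (199.0/4)(1 + √(1 + 4/19.9))² = 218.5, so 219. The plan's method is therefore the two-sided, continuity-corrected one. One-sided variants give 157 and 177.

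**2. Two-year probabilities.** With independent yearly risks and the reduction applied to each year:

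- Control: 1 − 0.90² = 19.0%
- Intervention: 1 − 0.95² = 9.75%

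**3. Sample size for 19.0% vs 9.75%.** d = 0.0925. n = (1.960 × 0.4962 + 0.842 × 0.4918)² / 0.00856 = 224.6, so 225. Corrected: 245.8, so 246. Like for like, the increase is 219 to 246 (27 per arm) or 199 to 225 (26 per arm). Setting 225 against 219 would mix methods.

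**4. Other way of applying the 50%.** Halving the two-year risk (19.0% vs 9.5%) needs 232 corrected (212 uncorrected), still above 219 (199).

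**5. Power for 19.0% vs 9.75%.** Uncorrected power is Φ{[d√n − zα√(2m(1−m))] / √(p1(1−p1) + p2(1−p2))}; the corrected version replaces d by d − 1/n.

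| Per arm | Corrected | Uncorrected | Exact logistic Wald |
|---|---|---|---|
| 219 | 0.75 | 0.79 | 0.79 |
| 250 | 0.81 | 0.84 | 0.84 |

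The exact column enumerates both binomial distributions. It agrees with the uncorrected column, which is therefore the closer guide to the planned test.

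**6. Room for loss within 250.**

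- Plan's method: (250 − 219)/250 = 12.4% falls to (250 − 246)/250 = 1.6%.
- Uncorrected: (250 − 199)/250 = 20.4% falls to (250 − 225)/250 = 10.0%.

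**7. Separate sensitivity: year-2 capture.** Interviews stop at 12 months, so year-2 overdoses are seen only through records. The documents state no capture rate, and the fractions c below are assumptions. Year 1 is taken as fully captured, capture as equal between arms, and loss as nil. For annual rate r, p1 = 1 − (1−r)(1−rc) and p2 = 1 − (1−r/2)(1−rc/2). Power at 250 per arm, corrected (uncorrected):

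| Assumed year-2 capture | r = 10% | r = 12.5% |
|---|---|---|
| 100% | 0.81 (0.84) | 0.89 (0.91) |
| 75% | 0.75 (0.79) | 0.85 (0.87) |
| 50% | 0.67 (0.72) | 0.78 (0.82) |

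The 12.5% is half the 25% heroin median that the plan cites, following its own assumption that the rate in pharmaceutical users is half that in heroin users.

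**The case against.** The strongest reply is that the error is small and already covered. Under the planned logistic test, power at 219 is 0.79 against a stated 0.80, and the trial plans 250, where it is 0.84. This stands: it is why no change in sample size is asked for.

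Next, the 10% is itself uncertain. The plan extrapolates it from lifetime rates and says its validity cannot yet be judged. At 11% a year, compounding gives 20.8% vs 10.7% and 223 per arm (203 uncorrected), almost cancelling the error. Aim 1 also allows follow-up beyond 24 months: at an assumed 27 months the need is 221. Both points show that the correction is modest beside the uncertainty in its inputs. They do not make doubling right for the rate and two-year period on which the plan bases its power.

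The figure of 246 rests on assumptions too. If yearly risks are correlated within a person (0.1 assumed), the rates are 18.1% vs 9.3% and the need is 259 (237). If 10% and 5% are read as hazards, it is 274 (252). The hazard reading fits the text less well, since the plan uses the heroin annual rate directly as a one-year proportion. So 246 should be quoted with its assumptions.

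On capture, Other analyses already plans to evaluate completeness of records and differences by arm. It does so through interview questions, however, and the last interview is at 12 months, so year 2 is not directly checked.

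A reader might infer that the stratum is underpowered, or that year-2 events will be missed on a scale that makes it so. The documents support neither. On the compounded rates 250 per arm keeps at least 0.80 with complete data, and no capture or loss rate is given from which a shortfall could be derived.

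**Conclusion.** The concern holds in a limited form. The statement that 219 per arm gives 0.80 power is wrong for pharmaceutical opioid users, because it doubles an annual risk for an outcome analysed as a probability. On the plan's own method the need is 246 (232 if the two-year risk is halved instead), and power at 219 is 0.75, or 0.79 under the planned test.

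The error alone does not underpower the stratum at 250 per arm. Its practical effect is on the margin: compounding uses 27 of the 31 extra participants per arm that were meant to raise power and absorb loss. These figures assume independent yearly risks, the reduction applied to each year, no loss and complete capture. The arithmetic is firm; the capture scenarios are illustrations only. Severity: minor to moderate.

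**What to change.** Keep n=500 in this stratum. In the Sample Size Calculation, give pharmaceutical opioid users their own statement, for example:

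> For pharmaceutical opioid users, assumed annual risks of 10% vs 5%, independent between years, give two-year probabilities of 19.0% vs 9.75%. Power of 0.80 needs 246 per arm with continuity correction (225 without). With 250 per arm, no loss and complete capture of events, power is 0.81 (0.84 without correction). If the two-year risk is halved instead (19.0% vs 9.5%), 232 per arm (212) are needed.

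Then add a separate sensitivity, labelled as assumed:

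> Overdoses in year 2 are observed only through records, and their capture rate is not known. At 250 per arm, power would be 0.75 (0.79) if 75% were captured and 0.67 (0.72) if 50% were. A true annual rate of 12.5% would give 0.89 (0.91) at full capture.

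It would also help to say in Aim 1 which source and time horizon define the event in each stratum, because the documents describe the period of records follow-up in different ways; the point does not depend on this.

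The cost is a few sentences, with no added participants and no design change. The stated power for this stratum becomes slightly less favourable.
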